5.2.4. Interim Analyses and Data Monitoring

There are 2 planned interim analyses: a blinded 8-week interim analysis (conducted after all subjects have completed the 8-week visit), and an unblinded 6-month interim analysis (conducted after all subjects have completed the 6-month visit and the study has been unblinded).

Neither of the planned interim analyses for this study is intended to be assessed with the purpose of altering the study design or sample size.

The 8-week interim analysis will include available data through the 8-week assessment including, but not limited to, primary efficacy and safety data. The individual treatment assignments will remain blinded at this time. The 8-week interim analysis will be assessed by the unblinded DSMB in accordance with the DSMB charter. Analysis will be conducted by the independent unblinded DSMB statistician. Only aggregate data, by treatment group, will be provided outside of the DSMB. Data will be cleaned to the extent possible but not locked for this analysis. All outstanding adjudications for events occurring with 8-weeks should be resolved. A separate interim analysis plan will provide additional details as to the content and dissemination of these results.

The 6-month interim analysis will include all available data through 6 months. The study will be unblinded for analysis at this time. The 6-month interim analysis results will help inform the appropriateness of the crossover.

5.2.5. Multicenter Studies

Consistency of the primary efficacy endpoint across study sites (centers) will be examined. Results will be presented by study site. There will be insufficient power to determine differences between sites, however, any notable differences between sites will be explored. Sites with less than 10 subjects may be combined by country in order to assess if there are statistical differences between sites. The interaction p-value from the ANOVA model for treatment by site will be calculated. A p-value < 0.15 will be viewed as evidence of differences between sites and will be discussed in the final study report.

Additionally, regions (US and Europe) will be pooled for the analysis by treatment group. Consistency of the effects by region will be explored by displaying the primary efficacy results by region. The interaction term for region by treatment will be calculated using analysis of variance. A treatment by region interaction p-value less than 0.15 will be explored further and described in the final study report.

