5.2.2. Adjustments for Covariates

Analysis of changes in blood pressure measures will be adjusted for baseline values using analysis of covariance (ANCOVA). Raw mean values will be presented, however, comparisons between groups will include the baseline value of the associated measure as described below. There is no other planned adjustment for covariates.

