5.4.1. Primary Efficacy Endpoint

The mean change in 24-hour ambulatory SBP from baseline to 8 weeks post-treatment will be presented in each group. The difference between groups will be summarized and compared using ANCOVA with adjustment for the baseline 24-hour ambulatory SBP.

The protocol defined window for the 8-week (56 day) visit is ± 7 days. For the purposes of analysis, measurements obtained within -15 days or ± 30 days (i.e., between 41 and 86 days) will be considered valid and will be analyzed as part of the primary endpoint analysis, provided that the subject remained off antihypertensive medication prior to collection of ABPM.

For the primary analysis, all available data will be used. There will be no imputation of data at 8 weeks. This analysis will be repeated in the PP analysis set.

In addition to the primary analysis, the following secondary and sensitivity analyses will be conducted:

- 1. Subjects who meet the protocol defined criteria for antihypertensive drug treatment and receive treatment within the 8 weeks prior to assessment of the primary endpoint will have their 8-week value imputed with their baseline value of ABPM.
- 2. Subjects who meet the protocol defined criteria for antihypertensive drug treatment and receive treatment within 8 weeks will be removed from the analysis.
- 3. Subjects who receive antihypertensive treatment within 8 weeks for any reason or in whom antihypertensive medications are detected via compliance samples will be removed from the analysis.
- 4. Missing data at 8 weeks will be imputed via multiple imputation techniques. The following covariates will be considered for the imputation: treatment group, age, gender, history of diabetes, BMI, anatomy defined by length from ostium to bifurcation, number of medications at baseline, baseline office systolic pressure, 8-week office systolic pressure, baseline 24-hour ambulatory SBP. These factors were chosen based on clinical experience and recent literature (Fengler, 2016) (Id, 2016) (Kandzari, 2015).
- 5. Missing data at 8 weeks and data for those subjects who meet the protocol defined criteria for antihypertensive drug treatment and receive treatment within 8 weeks will be imputed via multiple imputation techniques.

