7. CHANGES TO THE STATISTICAL ANALYSIS PLAN

Version / Date	Old Analysis	New Analysis	Reason for change
2.0 28Sep2020	n/a	Telephone contacts at 2 and 6 weeks in Ireland only added.	Updated per Protocol V6.0
		Those protocol deviations associated with COVID-19 will be additionally summarized separately.	Per FDA guidance
		Subgroups added:Region (US vs Europe)Ethnicity (US only)Race (US only)	Updated per Protocol V6.0
		Analysis windows clarified and description expanded	Clarification
		Added repeated measures analysis of blood pressure.	Oversight
3.0 08Dec2020	8-week primary analysis window not defined, assumed to be per the protocol	8-week primary analysis window expanded.	Addition, clarification
	No imputation specified for primary analysis	Imputation of data for subjects who meet the criteria for antihypertensive drug treatment for the primary analysis clarified.	Clarification
	n/a	Sensitivity analyses added for all 8-week BP measures	Addition
	n/a	Exploratory hierarchical analysis added	Addition
	Comparison between groups for BP measurements via t-test	Comparison between group for BP measures by ANCOVA adjusting for baseline BP	Per FDA guidance for the Target BPI study, and for consistency between the 2 studies
4.0 19Nov2021	n/a	Two unblinded team members (either two statisticians or a statistician and a statistical programmer) will be assigned for all analyses.	CAPA-00012

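### The site and region interaction tests are specified as ANOVA, while the primary endpoint is analysed by baseline-adjusted ANCOVA; read literally, they are a less precise check of the same interaction

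*SAP*

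**What the plan says.** SAP 5.2.5 (Multicenter Studies) sets two checks on the primary endpoint. For sites, with those under 10 subjects possibly combined by country, "The interaction p-value from the ANOVA model for treatment by site will be calculated". For regions, "The interaction term for region by treatment will be calculated using analysis of variance". Neither sentence mentions a baseline term. Each p-value carries a rule. For sites: "A p-value < 0.15 will be viewed as evidence of differences between sites and will be discussed in the final study report". For regions: "A treatment by region interaction p-value less than 0.15 will be explored further and described in the final study report".

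Elsewhere the SAP uses ANCOVA for the same outcome. Section 5.2.2 says that "comparisons between groups will include the baseline value of the associated measure", and 5.4.1 has the primary endpoint "compared using ANCOVA with adjustment for the baseline 24-hour ambulatory SBP". The change table in section 7 records when the t-test gave way to this in version 3.0: "Comparison between group for BP measures by ANCOVA adjusting for baseline BP". Section 3.4.1 still names the independent two-sample t-test for the primary endpoint.

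**The concern.** The SAP uses ANCOVA and ANOVA as separate terms, so a programmer who follows 5.2.5 as written would fit treatment, site (or region) and their interaction without baseline. The primary result would come from a different model.

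This has three consequences:

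- The interaction is estimated with more residual noise whenever baseline predicts change.
- Chance baseline imbalance between arms that differs from one site or region to another stays in the interaction estimate.
- Section 5.2.5 also promises the primary efficacy results by region. Under 5.4.1 those are baseline-adjusted, so the displayed effects and the p-value beside them could point in different directions.

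What is at stake is limited to the p<0.15 rule: what counts as evidence of a site difference and is discussed in the report, and whether a regional difference is explored further and described.

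**Working it through.** **Inputs from the documents (SAP 3.3 and 5.2.5).** SD of change 8 mmHg (10 and 12 also tabulated); 80 evaluable subjects, 40 per arm; 5 mmHg as a clinically meaningful main effect; threshold p<0.15 for each interaction.

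**Inputs not in the documents (assumed).** Two equal regions, so 20 per arm per region; a true regional difference in effect of 5 mmHg; equal variances at baseline and week 8; baseline/week-8 correlation ρ from 0.3 to 0.9.

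**The plan's own figure.** The SAP gives 80% power for 5.1 mmHg with SD 8 at two-sided 0.05. With 40 per arm the t-test calculation gives 80.4%, so the figure reproduces. It is main-effect power; no power is stated for the interaction tests.

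**Standard error of the region interaction.** The interaction is a difference of two treatment differences, so SE = SD × √(4/20).

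- ANOVA: 8 × √0.2 = 3.58 mmHg.
- ANCOVA: with equal variances σ², the variance of change is 2σ²(1−ρ) and the variance left after adjusting for baseline is σ²(1−ρ²). The ratio is (1+ρ)/2, so the SE is multiplied by √((1+ρ)/2).

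**Chance of p<0.15 for a true 5 mmHg regional difference** (noncentral F; 76 error df for ANOVA, 75 for ANCOVA):

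| Model | SE factor | SE (mmHg) | Chance |
|---|---|---|---|
| ANOVA | 1 | 3.58 | 48% |
| ANCOVA, ρ = 0.9 | 0.975 | 3.49 | 50% |
| ANCOVA, ρ = 0.7 | 0.922 | 3.30 | 53% |
| ANCOVA, ρ = 0.5 | 0.866 | 3.10 | 57% |
| ANCOVA, ρ = 0.3 | 0.806 | 2.88 | 61% |

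At larger SDs the gain is smaller: 38% against 39% to 48% at SD 10, and 31% against 32% to 39% at SD 12. With a 25:75 regional split and SD 8 it is 41% against 42% to 52%.

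**Sites.** With six pooled groups, a between-site SD of the treatment effect of 5 mmHg (both assumed) and SD 8, the chance is 73% with ANOVA and 75% to 88% with ANCOVA.

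**Where the gain vanishes.** If baseline has no slope on change, both tests give 48%. The equal-variance assumption also matters, because eligibility restricts baseline 24-hour SBP to 135–170 mmHg and week 8 is unrestricted. Suppose the baseline SD is 0.8 of the week-8 SD. The SE factor becomes √((1−ρ²)/(1+0.64−1.6ρ)):

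- ρ = 0.5: √(0.75/0.84) = 0.945, chance 51%.
- ρ = 0.7: √(0.51/0.52) = 0.990, chance 49%.
- ρ = 0.8: √(0.36/0.36) = 1, no gain.

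**Bias and false triggers.** In simulation (20,000 trials per setting, 80 subjects, two equal regions, SD of change 8, baseline truncated to 135–170 mmHg), both models averaged the true interaction. With no true interaction, both gave p<0.15 in about 15% of trials. When baseline predicted change (slopes of −0.3 to −0.7), the two models disagreed on the p<0.15 flag in 6% to 25% of trials.

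**The case against.** The strongest reply is that 5.2.5 never says baseline is left out. Section 5.2.2 is a general rule without a stated exception for site or region, and could be read as carrying the covariate into 5.2.5. That reading is possible, but 5.2.5 names a different model twice. The text supports either reading, and one clarifying sentence settles it.

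A reader might also infer more than the documents support:

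- **That baseline differences between regions or sites contaminate the interaction.** They do not when both arms share them. The outcome is already change from baseline, and a shared difference goes into the site or region main effect. Only chance imbalance between arms that varies by site or region remains, and randomization is stratified by site.
- **That the unadjusted test raises the risk of flagging mere imbalance.** The false-trigger rate is about 15% under both models.
- **That the tests address a different effect from the one reported.** Both models target the same interaction; the estimator differs, not the estimand.
- **That a missed p<0.15 hides a difference.** Section 5.2.5 presents results by site and region unconditionally, and says notable site differences will be explored. Tables 14.2.1-3, 14.2.1-6 and 14.2.1-9 show site, region and country whatever the p-value, and region and country are also subgroups in 5.2.7.

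It is also fair that the SAP disclaims formal hypothesis testing (5.2.1, 5.2.6) and concedes low power between sites. That limits the importance of the point. It is no reason to forgo precision from a measurement already collected and already in the primary model.

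**Conclusion.** The mismatch is in the current SAP text and is worth correcting, as a minor improvement. As written, the interaction tests use a less precise estimator than the primary model and can disagree with the adjusted effects displayed with them. No primary conclusion depends on these tests.

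Across the settings tried, ANOVA lowers the chance of reaching p<0.15 by between nothing and about 13 percentage points for region; for pooled sites the loss can be somewhat larger (73% against up to 88% in the case above). The size rests on a baseline/week-8 correlation, a regional split and a variance ratio that the documents do not give. The direction is firmer: apart from one degree of freedom, adding baseline cannot increase the residual variance.

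**What to change.** In SAP 5.2.5, take both interaction p-values from the primary ANCOVA: treatment, (pooled) site or region, their interaction, and baseline 24-hour ambulatory SBP. State that the effects displayed by region are baseline-adjusted, so that they match the p-value beside them. In the same edit, reconcile 3.4.1, which still names the two-sample t-test, with 5.4.1.

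The cost is SAP wording and a model statement in the programs. No new data, visits or subjects are needed, and the p<0.15 thresholds can stay as they are.

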5.2.6. Multiple Comparisons/Multiplicity

There is no formal hypothesis testing and thus no adjustment for alpha in necessary. In addition, there is a single primary endpoint in this study. Analyses of secondary endpoints are considered supportive. As such, there is no adjustment to alpha for multiplicity necessary to control Type I error.

5.2.7. Examination of Subgroups

The following subgroups will be presented for the primary efficacy endpoint in the ITT analysis set:

- Age grouped according to the median age
- Gender (male vs. female)
- Region (US vs Europe)
- Ethnicity (US only)
- Race (US only)
- Country
- Subjects who require a change of antihypertensive drugs during the post-procedure follow-up period
- Subjects with baseline ambulatory SBP > 140 mmHg and DBP < 90 mmHg versus all other subjects
- Subjects with baseline eGFR within the following groupings 45-60, 61-75, and >75 mL/min/1.73 m². Comparison of changes in eGFR will also be explored within this subgroup.

The following subgroup will be presented for the secondary efficacy endpoints in the ITT Analysis Set:

• Subjects with baseline daytime ambulatory SBP >140 mmHg and DBP <90 mmHg versus all other subjects.

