- 11 If the renal duplex ultrasound assessment at 6 months cannot be performed, or if the results are non-diagnostic, CTA/MRA/renal angiography may be performed if agreed with the sponsor (depending upon local regulatory approvals and site capacity). If renal artery stenosis of >60% or any other significant abnormality is suspected or confirmed by renal duplex ultrasound, as evaluated by the core laboratory, or as the result of other clinical assessments, those findings should be confirmed using the imaging modality used at screening (CTA/MRA/renal angiography). The choice of imaging may be changed at the discretion of the investigator and should be discussed with the sponsor.
- 12 Subjects with an eGFR of >45 and <60 mL/min/1.73 m² based on the screening serum creatinine sample will undergo blood sampling for post-contrast serum creatinine measurement 48-96 hours after imaging at screening. Subjects with an eGFR of >45 and <60 mL/min/1.73 m² based on the Week -1 (baseline) serum creatinine sample will undergo blood sampling for post-contrast serum creatinine measurement 48-96 hours after imaging during the procedure and any subsequent procedure where imaging contrast is used.
- 13 See Table 3 for details of blood and urine parameters. Tests to be done in the case of ET will be as for the Month 6 visit, but excluding compliance tests.
- 14 For measurement of serum creatinine only (all subjects). This sample must be taken prior to imaging at screening, because the eGFR value based on this measurement will be used to assess whether the subject is excluded or may proceed to have the screening imaging assessment.
- 15 Activated coagulation time (ACT) only is performed on Day 0, per the hospital's standard of care.
- 16 For compliance testing only.
- 17 No antihypertensive medications are permitted from the start of the run-in period until the subject has completed the visit at 8 weeks post-treatment (except in the case of emergencies).
- 18 Antihypertensive medications may be given after the 8-week visit if necessary (according to pre-defined criteria and proposed titration schedule).

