Appendix I Proposed Structured Drug Titration

After 8 weeks post-treatment, subjects may take antihypertensive medications to maintain a target office SBP of <140 mmHg and ≥ 90 mmHg (based on a mean of 3 measurements). The titration regimen provided in the following table should be followed if possible.

Step (Target SBP <140 mmHg and ≥ 90 mmHg) ¹	Drug	Treatment Score
0 (not needed)	None	0
1 (if needed)	CCB: mid-dose	1
2 (if needed)	ACE inhibitor or ARB: full dose	2
3 (if needed)	Hydrochlorothiazide 12.5 mg	3
4 (if needed)	Hydrochlorothiazide 25 mg	4
5 (if needed)	CCB: increase to full dose	5
6 (if needed)	Spironolactone or beta-blocker or clonidine	6
7 (if needed)	Spironolactone or beta-blocker or clonidine	7
8 (if needed)	Spironolactone or beta-blocker or clonidine	8

Abbreviations: ACE = angiotensin-converting enzyme; ARB = angiotensin receptor blocker; BP = blood pressure; CCB = calcium channel blocker; SBP = systolic blood pressure.

1 There will usually be 2 to 3 weeks between steps. If the target is reached, there are no further steps even if BP fluctuates above the target. For Steps 6, 7, and 8, the choice of drug and dose is at the investigator's discretion. If initial systolic BP is ≥ 160 mmHg, Steps 1 and 2 can be combined. Fixed-combination drug products can be used to decrease pill burden.

Source: Weber MA, Kirtane A, Mauri L, et al. Renal denervation for the treatment of hypertension: making a new start, getting it right. *J Clin Hypertens* 2015;17(10):743-50.

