2. INTRODUCTION

This statistical analysis plan (SAP) in conjunction with the table shells is intended to prospectively (a priori) outline the analyses and presentations of data that will form the basis for conclusions to be reached to answer the study objectives outlined in the protocol, and to explain in detail how the data will be handled and analyzed, adhering to commonly accepted standards and practices of biostatistical analysis in clinical trials. Results obtained from the analyses outlined in this document will be the basis of the Clinical Study Report for this study. This plan is based on Version 6.0 of the study protocol dated 01 July 2020.

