5.2. General Considerations

5.2.1. General Methods

Two unblinded team members (either two statisticians or a statistician and a statistical programmer) will be assigned for all analyses. This will allow for discussion of output and direct QC of statistical programming on the exact same dataset.

In general, continuous variables will be summarized with descriptive statistics (n, mean, SD, range, median, and interquartile range). The difference between groups will be presented and the normal approximation will be used to calculate two-sided 95% confidence intervals (CIs). Change from baseline, when relevant, will be computed as the paired mean difference and 95% CI of the mean difference at each time point.

For all continuous primary and secondary blood pressure endpoints, changes over time will be additionally explored in mixed effects repeated measures analyses, including the values at all time points.

Categorical variables will be summarized as frequencies and percentages. Relative risks and 95% CIs will be computed.

All statistical analyses will be performed using SAS® Version 9.4 or higher (SAS Institute, Cary, NC 27513, USA).

For each variable, the baseline value will be defined as the last value collected before the procedure.

There will be no formal hypothesis testing conducted in the study. Ninety-five percent CIs, when presented, are intended to be descriptive in nature only. For binary variables, CIs will be calculated via exact binomial methods. For continuous variables, the CI of the mean will be constructed using the normal approximation.

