6 (if needed)	Spironolactone or beta-blocker or clonidine	6
7 (if needed)	Spironolactone or beta-blocker or clonidine	7
8 (if needed)	Spironolactone or beta-blocker or clonidine	8

Abbreviations: ACE = angiotensin-converting enzyme; ARB = angiotensin receptor blocker; BP = blood pressure; CCB = calcium channel blocker; SBP = systolic blood pressure.

- 1. There will usually be 2 to 3 weeks between steps. If the target is reached, there are no further steps even if BP fluctuates above the target. If initial systolic blood pressure (SBP) is ≥160 mmHg, Steps 1 and 2 can be combined. Fixed-combination drug products can be used to decrease pill burden.
- 2. The treatment score will be used for the purpose of the statistical analysis.

Source: Weber et al. 2015

5.5.2.5. Use of Antihypertensive Medication(s) (including Increases/Decreases) from 8 weeks to 6 months Post-Treatment (Titrated According to Standardized Formula to Maintain a Target SBP of <140 mmHg and ≥90 mmHg).

The mean change in the number of antihypertensive medications will be summarized as described in Section 5.7 along with 95% CIs for the mean change in number of medications. The addition of new antihypertensive drugs will be considered an intensification of the antihypertensive regimen. Discontinuation of one or more of the baseline antihypertensive medications without an increase in dose of remaining drugs or addition of new drugs will be considered a reduction in antihypertensive drug regimen.

The mean treatment score will be reported by treatment group and the groups compared via Fisher's Exact test. These analyses will be conducted in the ITT and PP analysis sets.

5.5.2.6. Compliance with Not Taking Antihypertensive Medications Through 8 weeks Post-Treatment. The number and percent of patients in whom no antihypertensive medications are detected according to urine compliance results will be summarized by treatment group and compared using Fisher's Exact test. Subjects who meet the protocol defined criteria for antihypertensive drug treatment and receive treatment within 8 weeks will be excluded from the analysis. These analyses will be conducted in the ITT and PP analysis sets.

5.5.2.7. Use of Antihypertensive Medication(s) according to Defined Daily Dose.

In addition to the protocol specified analyses as described above, prescribed medications will be summarized according to the sum of the defined daily dose (DDD) in order to assess and

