9. STATISTICAL TABLES TO BE GENERATED

Disposition/Demographics

Table 14.1.1 Subject Disposition (Main Study)

Table 14.1.1 Subject Disposition (Crossover Phase)

Table 14.1.1-2 Screen Failures

Table 14.1.2-1 Baseline Demographics and Medical/Surgical History - ITT Analysis Set

Table 14.1.2-2 Baseline Demographics and Medical/Surgical History – Safety Analysis Set

Table 14.1.2-3 Baseline Demographics and Medical/Surgical History – PP Analysis Set

Table 14.1.3-1 Procedure Information - ITT Analysis Set

Table 14.1.3-2 Procedure Information - ITT Analysis Set

Table 14.1.3-3 Procedure Information RENAL ARTERY TREATMENT - ITT Analysis Set

Efficacy

Table 14.2.1-1 Primary Endpoint: 24-Hour Systolic Ambulatory Blood Pressure at 8 weeks - ITT Analysis Set

Table 14.2.1-2 Primary Endpoint: 24-Hour Systolic Ambulatory Blood Pressure at 8 weeks - PP Analysis Set

Table 14.2.1-3 Primary Endpoint: 24-Hour Systolic Ambulatory Blood Pressure at 8 weeks, by Site - ITT Analysis Set

Table 14.2.1-4 Primary Endpoint: 24-Hour Systolic Ambulatory Blood Pressure at 8 weeks, by Age - ITT Analysis Set

Table 14.2.1-5 Primary Endpoint: 24-Hour Systolic Ambulatory Blood Pressure at 8 weeks, by Gender - ITT Analysis Set

Table 14.2.1-6 Primary Endpoint: 24-Hour Systolic Ambulatory Blood Pressure at 8 weeks, by Region (US vs Europe) – ITT Analysis Set

Table 14.2.1-7 Primary Endpoint: 24-Hour Systolic Ambulatory Blood Pressure at 8 weeks, by Ethnicity (US only) – ITT Analysis Set

Table 14.2.1-8 Primary Endpoint: 24-Hour Systolic Ambulatory Blood Pressure at 8 weeks, by Race (US only) – ITT Analysis Set

Table 14.2.1-9 Primary Endpoint: 24-Hour Systolic Ambulatory Blood Pressure at 8 weeks, by Country – ITT Analysis Set

Table 14.2.1-10 Primary Endpoint: 24-Hour Systolic Ambulatory Blood Pressure at 8 weeks, by Subjects Receiving Treatment – ITT Analysis Set

Table 14.2.1-11 Primary Endpoint: 24-Hour Systolic Ambulatory Blood Pressure at 8 weeks, by Baseline Ambulatory SBP>140mmHg and DBP<90mmHg – ITT Analysis Set

Table 14.2.1-12 Primary Endpoint: 24-Hour Systolic Ambulatory Blood Pressure at 8 weeks, by eGFR – ITT Analysis Set

Table 14.2.2-1 24-Hour Ambulatory Blood Pressure at 8 weeks, 6 months and 1 Year ALL

AVAILABLE DATA - ITT Analysis Set

Table 14.2.2-2 24-Hour Ambulatory Blood Pressure at 8 weeks, 6 months and 1 Year ALL

AVAILABLE DATA - PP Analysis Set

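### One subgroup for the 8-week ambulatory SBP comparison is defined by a drug change after randomisation, so its within-stratum arm differences need not estimate the treatment effect

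*SAP*

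**What the plan says.** SAP 5.2.7 lists the subgroups to be shown for the primary endpoint in the ITT set. One of them is "Subjects who require a change of antihypertensive drugs during the post-procedure follow-up period". All the others are demographic, geographic or baseline factors. SAP section 9 plans the matching Table 14.2.1-10, whose title describes the split differently: "at 8 weeks, by Subjects Receiving Treatment".

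Three other parts of the plan bear on this:

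- **Timing.** Randomisation takes place on Day 0, after angiography (Protocol Table 1, footnote 21). The synopsis gives a follow-up period of 2 years.
- **What drives a drug change.** Protocol Appendix I: "After 8 weeks post-treatment, subjects may take antihypertensive medications to maintain a target office SBP of <140 mmHg". Protocol Table 1, footnote 18: "Antihypertensive medications may be given after the 8-week visit if necessary". Before the 8-week visit, drugs are allowed only in emergencies.
- **Drug use as an outcome.** Both documents list it among the secondary efficacy endpoints. SAP 5.5.2.5 is headed "Use of Antihypertensive Medication(s) (including Increases/Decreases) from 8 weeks to 6 months Post-Treatment", and 5.5.2.4 covers the first 8 weeks.

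**The concern.** Membership of this subgroup is known only after treatment has been given, and it depends on blood pressure, which treatment is meant to change. A treated subject who still needs drugs has stayed high despite treatment, whereas a sham subject who needs them has stayed high without it. Within either stratum the arms then differ in more than treatment, and randomisation no longer protects the comparison. On the natural reading of a 2-year follow-up period, an event that mostly comes later also sorts an outcome already measured at week 8.

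The risk is one of interpretation. Table 14.2.1-10 would sit among baseline subgroups with no visible caveat, and a reader could take its two rows as the effect of denervation in patients who did and did not need drugs. The trial is meant to judge whether the effect justifies a pivotal study, and it calls 5 mmHg clinically meaningful. Two rows that both fall short of the overall effect could mislead.

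**Working it through.** **1. Inputs from the documents.** SAP 3.3 gives SD 8 mmHg, a clinically meaningful difference of 5 mmHg and 80 evaluable subjects (taken as 40 per arm). It states 80% power for 5.1 mmHg. Check: noncentrality = 5.1 / (8 × √(2/40)) = 2.851; critical t on 78 df = 1.991; power = 0.804. The stated figure reproduces. The plan gives no figure for the drug-change subgroup.

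**2. Assumed inputs.** The documents do not give these: office SD 12; sham mean office SBP 145, 150 or 155; office effect -5 or -8; correlation ρ between office SBP and ambulatory change 0.3 to 0.7; drug change whenever office SBP is 140 or more. The true ambulatory effect is set at -5.

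**3. Formulas.** With a = (140 - arm's office mean) / 12, the mean ambulatory change in each arm is

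- with a drug change: arm effect + ρ × 8 × φ(a) / (1 - Φ(a))
- without: arm effect - ρ × 8 × φ(a) / Φ(a)

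**4. Central case** (sham office mean 150, office effect -5, ρ = 0.5).

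- Sham: a = -0.833, and 80% have a drug change. Means are 0.5 × 8 × 0.353 = +1.41 and -0.5 × 8 × 1.393 = -5.57.
- Treated: a = -0.417, and 66% have a drug change. Means are -5 + 0.5 × 8 × 0.553 = -2.79 and -5 - 0.5 × 8 × 1.081 = -9.32.
- Arm difference with a change: -2.79 - 1.41 = **-4.20**. Without: -9.32 + 5.57 = **-3.75**.
- Unsplit: sham 0.798 × 1.41 + 0.202 × (-5.57) = 0; treated 0.662 × (-2.79) + 0.338 × (-9.32) = -5.0. The ITT difference is still -5.

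A Monte Carlo run of 2,000,000 per arm gave -4.21 and -3.77.

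**5. Range over sham office means 145 to 155.**

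| Ambulatory effect | Office effect | ρ | With change | Without change |
|---|---|---|---|---|
| -5 | -5 | 0.3 | -4.41 to -4.64 | -4.19 to -4.32 |
| -5 | -5 | 0.5 | -4.02 to -4.40 | -3.66 to -3.87 |
| -5 | -5 | 0.7 | -3.63 to -4.16 | -3.12 to -3.42 |
| -5 | -8 | 0.7 | -2.70 to -3.53 | -2.05 to -2.56 |
| -5 | 0 | any | -5.0 | -5.0 |
| -5 | any | 0 | -5.0 | -5.0 |
| 0 | -5 | 0.3 to 0.7 | +0.36 to +1.37 | +0.68 to +1.88 |

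The bias therefore comes from the office effect together with the correlation. A zero ambulatory effect alone does not remove it.

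**6. Softer trigger.** Prescribing is permitted, not automatic. A simulation with ANCOVA on baseline, office effect -5 and a gradual trigger (logistic, slope 0.15 per mmHg around 140) gives -4.3 to -4.8 with a change and -4.2 to -4.7 without.

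**7. Against sampling error.** In the central case the strata hold about 32 sham and 26 treated subjects with a change, and 8 and 14 without. Taking SD 8, the 95% half-widths are 1.96 × 8 × √(1/31.9 + 1/26.5) = 4.1 and 1.96 × 8 × √(1/8.1 + 1/13.5) = 7.0 mmHg. The biases of 0.80 and 1.25 are well inside them.

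**8. If only changes before the 8-week ABPM count.** SAP 5.2.8 and 5.4.1 accept values in the widened 8-week window only if the subject was still off antihypertensive drugs. Read literally, this leaves the drug-change stratum empty or nearly so, although 5.4.1 also says that all available data are used. The no-change stratum then largely repeats sensitivity analyses 2 and 3. In analysis 2, subjects who meet the rescue criteria and "receive treatment within 8 weeks will be removed from the analysis".

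**The case against.** The best defence is that nothing rests on this table. SAP 5.2.7 only says the subgroups will be presented. SAP 5.2.1 rules out formal testing and says that confidence intervals "are intended to be descriptive in nature only". Interaction p-values are planned for site and region, not for this split. All of that stands, and it is why the point is minor. But calling an interval descriptive deals with testing. It does not change what the point estimate measures.

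The size is also assumption-driven. Office mean, SD, effect and correlation are not in the documents. One threshold does not represent discretionary titration over repeated visits, and no direct drug effect on ABPM is modelled. This stands too: the figures show the mechanism and do not predict a result.

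Three stronger readings are tempting, and the documents do not support them:

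- A reader might infer that the plan leaves the period and comparator undefined. The synopsis gives a 2-year follow-up, and the SAP is to be read "in conjunction with the table shells", which were not available here and may state the comparator.
- A reader might infer that the primary result or the decision to proceed is compromised. The unsplit ITT comparison does not use this split, and no decision is tied to the table.
- A reader might infer that the bias vanishes whenever treatment has no ambulatory effect, or that a sharp trigger at 140 with office effect -5 gives its ceiling. The last row and the -8 row of the table contradict both.

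**Conclusion.** The point holds as a minor one. SAP 5.2.7 and Table 14.2.1-10 condition the primary endpoint on an event that follows randomisation and is itself an efficacy outcome. If treatment changes office SBP, and office SBP is correlated with the ambulatory change, neither stratum's arm difference estimates the treatment effect.

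Under the stated assumptions the shortfall from -5 mmHg is about 0.4 to 1.4 with a drug change and 0.7 to 1.9 without, for an office effect of -5. It reaches 2.95 (5 - 2.05) for an office effect of -8 with correlation 0.7. It is zero if either the office effect or the correlation is zero. On the narrow pre-week-8 reading the table adds almost nothing to the sensitivity analyses already planned. That membership follows randomisation rests on no assumption; only the size of the bias does.

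**What to change.** Take this bullet out of SAP 5.2.7 and Table 14.2.1-10 out of the treatment-effect subgroups. Report drug change only as an outcome by arm, as SAP 5.5.2.4, 5.5.2.5 and 5.7 already plan.

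If the table must stay because it was pre-specified, align its title with 5.2.7, add the footnote *defined after randomisation; not an estimate of treatment effect*, and draw no treatment-effect conclusion from it.

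The cost is one descriptive table lost or relabelled. If the full protocol also lists this subgroup (only the synopsis was available here), removal should be recorded in SAP section 6 as a change from the protocol; the footnote route avoids that. No new data are needed, and no information on drug use by arm is lost.
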